### **9.3.4. Noninvasive Radiological Liver Fibrosis Measurements**

Noninvasive radiological methods to assess liver stiffness and steatosis via TE will be conducted at selected centers where the devices are available. Liver stiffness values (kPa) and CAP (dB/m) values (based on available data) will be summarized by treatment group using arithmetic summary statistics as described in Section 6.2.1 at Baseline and at each DB post-Baseline visit. Treatment groups will be compared using a ANCOVA model at each visit with change from Baseline as the dependent variable, including treatment group and Baseline fibrosis stage based on NASH CRN criteria, and randomization stratification factors as fixed effects and Baseline as a covariate.

The proportion of fibrosis improvement based on liver stiffness value will be summarized using arithmetic summary statistics as described in Section 6.2.1 by treatment group at Week 16 of the DB phase. Fibrosis improvement is defined as any reduction in liver stiffness value. Treatment groups will be compared using a Cochran–Mantel–Haenszel (CMH) test stratified by the

Baseline fibrosis stage based on NASH CRN criteria and randomization strata. Missing values will be considered a nonresponse.

The correlation of Baseline liver stiffness value with baseline fibrosis stage based on NASH CRN criteria (Stage 1, 2 or 3, 4) and modified Ishak scoring criteria (Stage 1, 2, 3, 4, 5, 6) based on biopsy will also be assessed using Spearman's rank correlation coefficient. Arithmetic summary statistics of Baseline liver stiffness by each fibrosis stage scoring will be presented. A box and whisker plot of the data also will be produced. The correlation analysis and corresponding plot will be performed using the ITT population.

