## 2. STUDY OBJECTIVES

The DB primary objective is to evaluate the effect of obeticholic acid (OCA) on low-density lipoprotein (LDL) metabolism in subjects with biopsy-confirmed nonalcoholic steatohepatitis (NASH) and to assess the ability of atorvastatin to modulate this effect.

The DB secondary objectives are:

- To evaluate the safety and tolerability of OCA alone and in combination with atorvastatin therapy in subjects with biopsy-confirmed NASH.
- To evaluate the effect of OCA with and without atorvastatin therapy, on
  - High-density lipoprotein (HDL), very low-density lipoprotein (VLDL), triglycerides (TG), total cholesterol, and apolipoprotein (Apo) concentrations
  - Components of the reverse cholesterol transport pathway

The DB exploratory objectives are:

- To evaluate the effect of OCA on:
  - Liver biochemistry, inflammation, and apoptosis
  - Markers of glucose metabolism including C-peptide, insulin, fasting plasma glucose, hemoglobin-specific A1c fraction (HbA1c), homeostatic model assessment – beta-cell function (HOMA- $\beta$ ), and homeostatic model assessment – insulin resistance (HOMA-IR)
  - Anthropometric measures including height (measured at Screening Visit 1 only), weight, waist and hip circumference measurements, body mass index (BMI), and waist-to-hip ratio calculations
  - Cardiovascular risk scores (eg, Framingham Risk Score [FRS] and Reynolds score)

- To evaluate the pharmacokinetics (PK) and pharmacodynamics (PD) of OCA and its conjugates
- To evaluate the bioanalytical concentrations of atorvastatin and its metabolites
- To evaluate improvement in noninvasive-radiological assessment of fibrosis via transient elastography (TE; at sites where available)

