### 3.3.8. Noninvasive Radiological Liver Fibrosis Measurements

Noninvasive radiological methods to assess liver stiffness and steatosis will be conducted via transient elastography (TE) at selected centers where the devices are available.

- Observed liver stiffness values and change from Baseline at each DB post-Baseline visit
- Proportion of subjects with any reduction in liver stiffness value (kPa) at Week 16
- Observed controlled attenuation parameter (CAP) (dB/m) values and change from Baseline at each DB post-Baseline visit
- Both liver stiffness and CAP values are median values based on number of valid measurements

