## 8. STUDY POPULATION

### 8.1. Subject Disposition

Subject disposition information will be summarized and listed for all subjects. Summaries will include the following: the number of subjects randomized, the number of subjects in each analysis population, the number of subjects at each study site, the number of subjects completing the DB phase (Week 16) and each scheduled visit (Week 2, 4, 8, and 12), the primary reason for discontinuation from the DB phase, and the number of subjects enrolling in the LTSE. A subject will be considered as completing the DB phase if the subject has non-missing assessment of LDL metabolism at all scheduled visits (Weeks 2, 3, 4, 12, and 16). Percentages will be based on the ITT Population.

The reasons for discontinuation of investigational product (OCA/PBO) and discontinuation of study atorvastatin will be summarized in a similar manner.

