14.2.3.1.2	EE	Summary of VLDL Cholesterol Concentration – CV Units
14.2.3.1.3	EE	Summary of VLDL Cholesterol Particle Size and Particle Concentration
14.2.3.2.1	ITT	Summary of VLDL Cholesterol Concentration – SI Units (MMRM)
14.2.3.2.2	ITT	Summary of VLDL Cholesterol Concentration – CV Units (MMRM)
14.2.3.2.3		Summary of VLDL Cholesterol Particle Size and Particle Concentration (MMRM)
14.2.4.1	EE	Summary of Total Cholesterol and Triglyceride Concentrations – SI Units
14.2.4.2	EE	Summary of Total Cholesterol and Triglyceride Concentrations – CV Units
14.2.5	EE	Summary of ApoA1, ApoB, ApoE, ApoCII, ApoCIII and Lp(a) Concentrations
14.2.6	EE	Summary of Reverse Cholesterol Metabolism
14.2.7	EE	Summary of Liver Biochemistry and Markers of Liver Function
14.2.8	EE	Summary of Liver Inflammation, Hepatic Apoptosis, and Fibrosis
14.2.9.1	EE	Summary of Glycemic Control
14.2.9.2	EE	Summary of Glycemic Control by Diabetes Status
14.2.10	EE	Summary of Liver Stiffness Measurements via Transient Elastography
14.2.11	EE	Summary of Liver Fibrosis Improvement via Transient Elastography
14.2.12.1	EE	Summary of Correlation Between Liver Stiffness via Transient Elastography and Liver Biopsy NASH CRN Criteria
14.2.12.2	EE	Summary of Correlation Between Liver Stiffness via Transient Liver Elastography and Liver Biopsy Modified Ishak Scoring Criteria
14.2.13.1	EE	Summary of FIB-4 Score
14.2.13.2	EE	Summary of APRI Score
14.2.13.3	EE	Summary of NFS Score
14.2.13.4	EE	BARD Score Shift from Baseline
14.2.14.1	EE	Summary of Anthropometric Measures and Blood Pressure
14.2.14.2	EE	Summary of Anthropometric Measures and Blood Pressure by Diabetes Status
14.2.14.3	EE	Summary of Blood Pressure by Antihypertensive Use
14.2.15.1	EE	Summary of Cardiovascular Risk Scores
14.2.15.2.1	EE	Summary of Cardiovascular Markers of Risk – SI Units
14.2.15.2.2	EE	Summary of Cardiovascular Markers of Risk – CV Units
14.2.16.1	PK	Summary of Plasma Concentrations for OCA, Glyco-OCA, Tauro-OCA, and Total OCA by Treatment and Visit
14.2.16.2	PK	Summary of PK Parameters for OCA, Glyco-OCA, Tauro-OCA, and Total OCA by Treatment and Visit

Table Number	Population	Table Title
14.2.17.1	APK	Summary of Week 16 Plasma Concentrations for Atorvastatin, 2OH-Atorvastatin, and 4OH-Atorvastatin by Treatment
14.2.17.2	APK	Summary of Week 16 PK Parameters for Atorvastatin, 2OH-Atorvastatin, and 4OH-Atorvastatin by Treatment
14.2.18.1	ITT	Summary of Total Bile Acids and Total Endogenous Bile Acids

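### The Week 16 liver-stiffness improvement proportion sets missing elastography to nonresponse without limiting the denominator to subjects who had a Baseline elastography

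*SAP*

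**What the plan says.** SAP Section 9.3.4 opens with the scope of the measurement: "Noninvasive radiological methods to assess liver stiffness and steatosis via TE will be conducted at selected centers where the devices are available". Sections 2 and 3.3.8 carry the same limit.

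The endpoint in Section 3.3.8 is "Proportion of subjects with any reduction in liver stiffness value (kPa) at Week 16", and Section 9.3.4 defines the responder: "Fibrosis improvement is defined as any reduction in liver stiffness value". The arms are compared by a stratified CMH test, with the rule "Missing values will be considered a nonresponse".

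Appendix A lists Table 14.2.11, "Summary of Liver Fibrosis Improvement via Transient Elastography", under the EE Population. Section 7.4 makes EE membership depend on completing the double-blind phase at the indicated doses without relevant major deviations. Completion is defined in Section 8.1 by lipid data alone: "A subject will be considered as completing the DB phase if the subject has non-missing assessment of LDL metabolism at all scheduled visits". Section 7 defines no population for TE.

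Three other statements bear on the point:
- Section 9 says efficacy analyses rest on observed values and that nothing is to be imputed. Section 6.3.2 says the same of the primary analysis of efficacy endpoints.
- Sections 6.2.2 and 6.3.4 take percentages over non-missing data by default, but give way where another rule or an imputation is specified.
- Within Section 9.3.4, the limit to available data is attached only to the continuous stiffness and CAP summaries.

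**The concern.** A nonresponse rule suits subjects who could have been assessed and were not. Here the value may also be missing because the center has no device, or because there was no Baseline TE from which to compute a reduction. Neither says anything about response, yet nothing in Section 9.3.4 keeps such subjects out of the denominator.

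The EE Population sharpens this. Its members by definition have lipid data through Week 16, so drop-out should explain few of the missing Week 16 TE values. Subjects who were never measurable may well make up most of them.

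At stake are the improvement percentage printed for each arm, which a reader would take as an improvement rate, and the precision of the comparison. There is also a reproducibility problem. Section 6.1 relies on independent programming, and two programmers could choose different denominators from this text, one following Section 9.3.4 and the other Section 9.

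**Working it through.** **Plan's own figures.** The plan states no coverage, rate or power for this endpoint. Its only design figure (Section 5: 22 mg/dL, SD 24, n = 20, two-sided 0.05) concerns LDLc. It reproduces with a one-sample t-test (power 0.9729) and has no bearing here.

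**Does the text exclude unmeasured subjects?**

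| Place in SAP | Effect on a subject with no TE |
|---|---|
| 9.3.4, scope | TE not done at that center |
| 9.3.4, responder rule | missing is nonresponse; no Baseline TE required |
| 7.4, 8.1 | can be in EE without any TE |
| 6.2.2, 6.3.4 | default denominators yield to the specified rule |
| 9 | observed data only, so the subject would drop out |

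Only Section 9 would remove the subject, and it contradicts the specific rule in 9.3.4.

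**Size of the effect.** Let f be the share of an arm's EE subjects with TE and p the true improvement rate. Assume no Week 16 losses among measured subjects. Then reported rate = f × p. Coverage, true rates and 20 EE subjects per arm are all assumptions; Section 5 plans 20 per group.

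*One arm, p = 50%:* f = 25%, 50%, 75% gives 12.5%, 25%, 37.5%.

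*Two arms, true 60% vs 30%, equal coverage.* Power is Φ[(d − 1.96·SE0)/SE1], where d is the difference, SE0 the pooled and SE1 the unpooled standard error. As written n = 20 per arm; measured only n = 20f.

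| f | Reported | Difference as written | Difference measured only | Power as written | Power measured only |
|---|---|---|---|---|---|
| 75% | 45% vs 22.5% | 22.5 points | 30 points | 0.32 | 0.37 |
| 50% | 30% vs 15% | 15 points | 30 points | 0.20 | 0.26 |
| 25% | 15% vs 7.5% | 7.5 points | 30 points | 0.11 | 0.15 |

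*Second contrast, true 70% vs 45%, f = 50%:*
- Measured only, 10 per arm: z = 0.25 / √(0.021 + 0.02475) = 1.17.
- As written, 20 per arm, 35% vs 22.5%: z = 0.125 / √(0.01138 + 0.00872) = 0.88, about 25% lower.

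**Chance imbalance in coverage.** Section 4 stratifies randomization by LDLc and fibrosis stage, not by center. At f = 50%, p = 50%, 20 per arm and no treatment effect:
- Variance of the arm difference as written: 2 × 0.25 × 0.75 / 20 = 0.01875 (SD 13.7 points).
- Part due to coverage: 0.5² × 2 × 0.25 / 20 = 0.00625 (SD 7.9 points).
- Share: 0.00625 / 0.01875 = one third.

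The 7.9 points lie inside the 13.7 and are not added to them. As an illustration, 60% vs 40% coverage with a true 50% in both arms is reported as 30% vs 20%.

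**The case against.** **The authors may have meant something narrower.** The scope sentence of Section 9.3.4 confines TE to certain centers, so a missing value could mean a planned TE that was not obtained. If Section 9 governs, unmeasured subjects drop out altogether. This stands as a possible intent, so a reader should not infer that the sponsor will certainly count every unmeasured subject as a failure. But the SAP states neither limit, and the conflict with Section 9 has to be resolved whichever was meant.

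**The EE label is weak evidence.** Section 9 assigns EE to primary and secondary efficacy, and TE is exploratory, so the link rests on Appendix A. That appendix has errors nearby: it labels Tables 14.2.12.1 and 14.2.12.2 as EE where Section 9.3.4 says ITT, and it keeps atorvastatin PK tables that Section 12 drops. This is fair, but ITT membership does not require TE either, so the denominator problem is the same under that label.

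**Stronger readings that the document does not support.**
- A reader might infer that the TE objective goes unanswered. It does not: the stiffness and CAP summaries on available data and the ANCOVA of change do not use the nonresponse rule.
- A reader might infer bias between arms. Device availability is a property of the site, so randomization makes it independent of arm in expectation; imbalance is chance variation.
- A reader might infer that the proportion mostly measures device availability. At 75% coverage and a true 50%, 25 points are unmeasured and 37.5 points are true non-improvers.

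**The practical loss is small.** The comparison is underpowered either way, and Section 6.2.8 treats all p-values as descriptive. This limits the importance of the point but does not make the printed proportions correct.

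**Conclusion.** The concern holds as a denominator and missing-data fault in one exploratory table, together with an unreconciled conflict between Sections 9 and 9.3.4. Under the literal rule, each arm's improvement proportion is understated by the factor f, and with equal coverage the arm difference is diluted by the same factor. Across the assumed 25% to 75% coverage, a true 30-point difference shows as 7.5 to 22.5 points. Approximate power is 0.04 to 0.06 lower than with measured subjects alone, despite the larger nominal n.

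These sizes rest on assumed coverage and rates; at coverage near 100% the effect vanishes. The point merits correction because the reported percentages would be wrong as improvement rates, but it touches no primary or secondary result.

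**What to change.** In Section 9.3.4 and Table 14.2.11:
- restrict the improvement proportion and the CMH test to subjects with a valid Baseline TE;
- apply nonresponse only when such a subject's Week 16 value is missing;
- report the number with a Baseline TE by arm as the denominator.

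In Section 9, state that this is the one exception to the observed-data rule. The SAP already has a model for a measurement limited to selected sites: OCA sampling (Section 10.1) has its own population, which requires at least one confirmed fasted concentration (Section 7.5).

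The cost is a sentence in each of two sections and a changed denominator in one table. No new data are needed. The downside is a smaller stated n.

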## **8.3. Demographic and Baseline Characteristics**

Demographic variables will include the following:

- Age at informed consent
- Age at informed consent categorized as < 65 years and  $\geq$  65 years
- Sex
- Race/ethnicity

Other Baseline characteristics will include the following:

- Weight (kg)
- Height (cm) at Screening visit
- BMI ( $\text{kg}/\text{m}^2$ )
- BMI categorized as < 30  $\text{kg}/\text{m}^2$  and  $\geq$  30  $\text{kg}/\text{m}^2$
- Liver fibrosis stage using NASH Clinical Research Network (CRN) scoring criteria categorized as Stage 1a, 1b, 1c, 2, 3, 4
- Liver fibrosis stage using NASH CRN scoring criteria categorized as Stage 1, 2 and Stage 3, 4
- Liver fibrosis stage using modified Ishak scoring criteria categorized as Stage 1, 2, 3, 4, 5, 6
- NAFLD Activity Score (NAS) and its components categorized as:
  - Steatosis: 0, 1, 2, 3
  - Hepatocellular Ballooning: 0, 1, 2
  - Lobular Inflammation: 0, 1, 2, 3
- NAS categorized as < 6 and  $\geq$  6 total points
- Diabetes status: Yes, No (defined as subjects with any condition in the Endocrine/Metabolic body system and medical term containing “diabetes type II” or

similar derivative, as collected on the eCRF Medical History; if unable to determine what type of diabetes, set diabetes status to yes)

- Concomitant medication use (ongoing on Day 1. If it cannot be determined whether the medication was ongoing at the Day 1 visit due to a partial start or stop date, then it will be counted as ongoing.)
  - Vitamin E (ATC codes = 'A11HA' and Trade name = 'E VITAMIN')
  - TZD (ATC codes starting with 'A10BG')
  - Antidiabetic medication (ATC codes starting with 'A10')
  - Antihypertension medication (ATC codes starting with 'C02')
- Screening fasted serum LDL cholesterol concentration categorized as  $\leq$  and  $> 125$  mg/dL
- Screening HDL cholesterol concentration (mg/dL) categorized as  $\geq$  lower limit of normal (LLN),  $<$  LLN
- Baseline liver function test results as a continuous variable and categorized as follows by the LLN and the upper limit of normal (ULN) unless otherwise specified:
  - ALT:  $\leq 40$  U/L,  $> 40$  U/L and  $\leq$  ULN,  $>$  ULN
  - AST:  $\leq 40$  U/L,  $> 40$  U/L and  $\leq$  ULN,  $>$  ULN
  - Direct Bilirubin:  $\leq$  ULN,  $>$  ULN
  - Total Bilirubin:  $\leq$  ULN,  $>$  ULN
  - Platelets:  $\geq$  LLN,  $<$  LLN

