### List of Figures

Figure Number	Population	Figure Title
14.2		Efficacy Data
14.2.1.1	ITT	Baseline Liver Stiffness Measurements versus Baseline NASH CRN Liver Biopsy Stage
14.2.1.2	ITT	Baseline Liver Stiffness Measurements versus Baseline Modified Ishak Liver Biopsy Stage
14.2.1.1	PK	Individual Plasma Concentration of Unconjugated OCA Over Time
14.2.1.2	PK	Individual Plasma Concentration of Glyco-OCA Over Time
14.2.1.3	PK	Individual Plasma Concentration of Tauro-OCA Over Time
14.2.1.4	PK	Individual Plasma Concentration of Total OCA Over Time
14.2.2.1	PK	Mean (SD) Plasma Concentration of Unconjugated OCA Over Time by Dose (linear and semi-log plots)
14.2.2.2	PK	Mean (SD) Plasma Concentration of Glyco-OCA Over Time by Dose (linear and semi-log plots)
14.2.2.3	PK	Mean (SD) Plasma Concentration of Tauro-OCA Over Time by Dose (linear and semi-log plots)
14.2.2.4	PK	Mean (SD) Plasma Concentration of Total OCA Over Time by Dose (linear and semi-log plots)
14.2.3.1	PK	Boxplots of $AUC_{0-6}$ and $C_{max}$ versus Dose for OCA, Glyco-OCA, Tauro-OCA, and Total OCA by Visit (Day 1 and Week 16)
14.2.4.1.1	PK	Scatter Plot of Week 16 LDL Cholesterol Concentration versus Total OCA $AUC_{0-6}$ – SI Units
14.2.4.1.2	PK	Scatter Plot of Week 16 LDL Cholesterol Concentration versus Total OCA $AUC_{0-6}$ – CV Units
14.2.4.2.1	PK	Scatter Plot of Week 16 Change from Baseline in LDL Cholesterol versus Total OCA $AUC_{0-6}$ – SI Units
14.2.4.2.2	PK	Scatter Plot of Week 16 Change from Baseline in LDL Cholesterol versus Total OCA $AUC_{0-6}$ – CV Units
14.2.4.3.1	PK	Scatter Plot of Week 16 LDL Particle Size versus Total OCA $AUC_{0-6}$
14.2.4.3.2	PK	Scatter Plot of Week 16 Change from Baseline in LDL Particle Size versus Total OCA $AUC_{0-6}$
14.2.4.4.1	PK	Scatter Plot of Week 16 LDL Particle Concentration versus Total OCA $AUC_{0-6}$
14.2.4.4.2	PK	Scatter Plot of Week 16 Change from Baseline in LDL Particle Concentration versus Total OCA $AUC_{0-6}$
14.2.4.5.1	PK	Scatter Plot of Week 16 FGF-19 versus Total OCA $AUC_{0-6}$
14.2.4.5.2	PK	Scatter Plot of Week 16 Change from Baseline in FGF-19 versus Total OCA $AUC_{0-6}$
14.2.4.6.1	PK	Scatter Plot of Week 16 C4 versus Total OCA $AUC_{0-6}$

Figure Number	Population	Figure Title
14.2		Efficacy Data
14.2.4.6.2	PK	Scatter Plot of Week 16 Change from Baseline in C4 versus Total OCA AUC 0-6
14.2.4.7.1	PK	Scatter Plot of Week 16 CRP versus Total OCA AUC 0-6

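### The stiffness–biopsy correlation groups NASH CRN stage into two levels, which caps its Spearman coefficient; separately, its tables are labelled EE where the text and figures say ITT

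*SAP*

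**What the plan says.** Section 9.3.4 relates Baseline liver stiffness to two biopsy scorings. The first is "baseline fibrosis stage based on NASH CRN criteria (Stage 1, 2 or 3, 4"), the second "modified Ishak scoring criteria (Stage 1, 2, 3, 4, 5, 6) based on biopsy". Both relations "will also be assessed using Spearman's rank correlation coefficient".

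The CRN grouping is the randomization stratum of section 4, also used as a model covariate in section 6.2.3. It is not a limit of the data: section 8.3 lists "Liver fibrosis stage using NASH Clinical Research Network (CRN) scoring criteria categorized as Stage 1a, 1b, 1c, 2, 3, 4" and gives the two-group split as a separate item.

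On the population, section 9.3.4 says: "The correlation analysis and corresponding plot will be performed using the ITT population". In Appendix A the two correlation tables are 14.2.12.1, "Summary of Correlation Between Liver Stiffness via Transient Elastography and Liver Biopsy NASH CRN Criteria", and 14.2.12.2, "Summary of Correlation Between Liver Stiffness via Transient Liver Elastography and Liver Biopsy Modified Ishak Scoring Criteria". Both have EE in the population column. The matching figures, 14.2.1.1 ("Baseline Liver Stiffness Measurements versus Baseline NASH CRN Liver Biopsy Stage") and 14.2.1.2 (the Ishak counterpart), have ITT. These two figure numbers are used again for PK plots, so the figures meant here are best identified by title.

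**The concern.** Spearman's coefficient works on ranks. When one variable has only two values, all subjects within a group are tied, and even a perfect monotone relation cannot give a coefficient near 1. The grouped CRN stage discards the ordering of 1 against 2 and of 3 against 4; Ishak, scored over six levels, loses far less. Both coefficients will be reported for the same stiffness measurements, and part of any gap between them would come from the coding.

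The population labels are a different matter. If the tables are produced as labelled, the coefficients come from EE and the plots from ITT. EE (section 7.4) requires completing the double-blind phase on the indicated doses of investigational product and atorvastatin without relevant major deviations. Completion and dosing have no bearing on whether stiffness tracks biopsy stage at Baseline.

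**Working it through.** The SAP gives no figure for this correlation, so there is none to reproduce.

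**Inputs from the SAP.** CRN in two levels, Ishak in six, Spearman (9.3.4); individual CRN stages available (8.3); about 80 subjects enrolled (4); transient elastography at selected centers only (9.3.4).

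**Assumptions, because the SAP does not give them.** Shares of CRN stages 1/2/3/4 in four versions (table below); latent stiffness–stage correlation from 0.3 to 0.85; Ishak as six equally frequent levels.

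**Step 1: the ceiling.** For a continuous variable against an ordinal one with level shares p_i, the largest attainable tie-corrected Spearman coefficient in large samples is sqrt(1 − Σ p_i³). For two levels with shares p and q, 1 − p³ − q³ = 3pq, so the ceiling is sqrt(3pq). Its maximum, at p = q = 0.5, is sqrt(0.75) = 0.866.

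| Stage shares 1/2/3/4 (%) | Two levels | Four levels |
|---|---|---|
| 25/25/25/25 | sqrt(3 × 0.5 × 0.5) = 0.866 | sqrt(1 − 0.0625) = 0.968 |
| 40/30/20/10 | sqrt(3 × 0.7 × 0.3) = 0.794 | sqrt(1 − 0.100) = 0.949 |
| 50/30/15/5 | sqrt(3 × 0.8 × 0.2) = 0.693 | sqrt(1 − 0.1555) = 0.919 |
| 15/25/40/20 | sqrt(3 × 0.4 × 0.6) = 0.849 | sqrt(1 − 0.091) = 0.953 |

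Six equal Ishak levels give sqrt(1 − 6/216) = 0.986.

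**Step 2: attenuation below the ceiling.** Bivariate normal data (400,000 draws) were generated and the same latent stage was cut into two, four or six levels. At latent correlation 0.5 the coefficients were 0.35–0.40 with two levels, 0.44–0.46 with four and 0.47 with six. Over all scenarios:

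- two-level to four-level CRN: ratio 0.77–0.88, so about 12–23% lower;
- two-level CRN to six-level Ishak, for an identical underlying relation: ratio 0.72–0.86, so about 14–28% lower.

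The direction was the same in every scenario.

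**Step 3: absolute size in a sample of plausible size.** With an assumed 40 subjects and shares 30/30/25/15%, the mean coefficients for two, four and six levels were 0.31, 0.36 and 0.37 at latent correlation 0.4, and 0.47, 0.55 and 0.56 at 0.6. The two-to-four-level shift is thus 0.05 to 0.08.

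**Step 4: the population labels.**

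| Place | Population |
|---|---|
| Section 9.3.4, correlation and plot | ITT |
| Tables 14.2.12.1 and 14.2.12.2 | EE |
| Stiffness-by-stage figures 14.2.1.1 and 14.2.1.2 | ITT |

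Section 7.4 repeats efficacy analyses on ITT only if more than 20% of ITT subjects have the relevant deviations. With about 80 subjects, up to 0.20 × 80 = 16 could have them without triggering that repeat. How many of these would have elastography data is unknown.

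**The case against.** The two-level split has a rationale: it is the stratification grouping and a listed Baseline category. Elastography is done only at selected centers, so single stages may be sparse; 15% of 40 subjects is 6. The coefficient is also not the only display, since stiffness summaries by stage and a box plot are planned. All of this is fair, but Spearman's coefficient does not need well-filled categories, and the split can be kept for description. If the CRN phrase was meant as four separate stages, the wording still needs correcting.

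A shift of 0.05–0.08 is smaller than the sampling error of one coefficient at 40 subjects, roughly 1/sqrt(39) = 0.16 under no correlation. That stands as a limit on importance. The shift is nevertheless systematic, and it is avoidable.

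A reader might infer that Ishak will appear superior to CRN purely because of grouping. The SAP does not support this. It plans no test or ranking of the two scorings, they are different scales, and coding explains only part of any gap. A reader might also argue from lost power, but section 6.2.8 treats p-values and confidence intervals as descriptive, so no decision depends on it.

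On the population, text and figures agree on ITT, so the EE label is probably a slip in the table list. That limits the harm but does not remove the contradiction. The general EE-first rule of section 9 does not resolve it either, because section 9.3.4 makes an explicit exception for this analysis.

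**Conclusion.** Both defects hold, independently of each other, and both are minor.

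The two-level coding caps the CRN coefficient at 0.866 or less. That bound is algebraic and needs no assumption about the data beyond large samples. The range of 0.69–0.87, the 12–23% understatement relative to four levels and the 14–28% gap to Ishak rest on assumed stage shares and latent correlations.

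The table labels contradict the text and the figures, which leaves open which subjects enter the coefficient. It would be tempting to read this conflict as a further cause of the attenuation or of the CRN–Ishak gap. It is neither: both tables carry the same EE label, so the two coefficients would come from the same population.

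The analysis is exploratory, is not among the elastography endpoints listed in section 3.3.8, and touches no primary or secondary result.

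**What to change.** - In section 9.3.4, compute Spearman's coefficient with NASH CRN stage as ordered 1, 2, 3, 4 (1a, 1b and 1c pooled as stage 1). Keep the two-level split as a descriptive grouping only.
- In Appendix A, label Tables 14.2.12.1 and 14.2.12.2 as ITT subjects with a Baseline stiffness value, in line with the text and figures.
- Add a sentence that the CRN and Ishak coefficients are not to be ranked against each other. Four CRN levels and six Ishak levels still have slightly different ceilings (0.92–0.97 against 0.986 under the assumptions above).

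The cost is a change of wording and two table labels, with no new data. The only downside is that single stages may hold few subjects, which affects the by-stage summaries more than the coefficient.
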